10.1.2. Financial Disclosure

Investigators and Sub-Investigators will provide Alexion with sufficient, accurate financial information as requested to allow Alexion to submit complete and accurate financial certification or disclosure statements to the appropriate regulatory authorities. Investigators are responsible for providing information on financial interests during the course of the study and for 1 year after completion of the study.

Page 62 of 97
Alexion Confidential

10.1.3. Informed Consent Process

- It is the responsibility of the Investigator or designee to obtain signed (written or electronic signature) informed consent from all study participants prior to performing any study-related procedures including screening assessments.
- The Investigator or designee will explain the nature of the study (including but not limited to the objectives, potential benefits and risks, inconveniences, and the participant's rights and responsibilities) to the participant or his/her legally authorized representative, defined according to local and country regulations where the study is taking place, and answer all questions regarding the study.
- Participants must be informed that their participation is voluntary. Participants or their legally authorized representative will be required to sign a statement of informed consent or a certified translation, if applicable, that meets the requirements of 21 CFR 50, local regulations, EU General Data Protection Regulation (GDPR), ICH GCP guidelines, Health Insurance Portability and Accountability Act (HIPAA) requirements, where applicable, and the IRB/IEC or study center.
- The participant's medical record must include a statement that signed (written or electronic) informed consent was obtained before any screening procedures were performed with a participant, and the date the written consent was obtained. The authorized person obtaining the informed consent must also sign the ICF(s).
- Participants must be reconsented to the most current version of the ICF(s) during their participation in the study, as applicable.
- A copy of the signed (written or electronic) informed consent documentation (ie, a complete set of participant information sheets and fully executed signature pages) must be provided to the participant or the participant's legally authorized representative, as applicable. This document may require translation into the local language. Original signed (written or electronic) consent forms must remain in each participant's study file and must be available for verification at any time.

Participants who are rescreened outside of the screening window are required to sign a new ICF (see Section 5.4).

10.1.4. Data Protection

- Participants will be assigned a unique identifier by Alexion. Any participant records or datasets that are transferred to Alexion will contain the identifier only; participant names, initials, or any information which would make the participant identifiable will not be transferred.
- Participants must be informed that their personal study-related data will be used in accordance with applicable data protection law, and participants must also be informed of any individuals rights they may have with regard to their personal data. Participants will be informed about how their personal study-related data will be disclosed, and will be required to agree to the information contained in the informed consent and provide consent to the processing of their personal data, if required by applicable data protection law.

- Participants must be informed that their medical records may be examined by Clinical Quality Assurance auditors or other authorized personnel appointed by Alexion, appropriate IRB/IEC members, and inspectors from regulatory authorities.
- Alexion as a data controller has implemented privacy and security controls designed to help protect participant personal data, including information security controls, firewalls, incident detection, and secure transfer measures.
- In the event of any accidental or unlawful destruction, loss, alteration, unauthorized disclosure of, or access to, personal data ("breach"), the controller has implemented procedures and measures to promptly address and mitigate any risk to the data participant. In the event of a breach, the controller will notify the appropriate regulatory authorities and/or the data participant in accordance with applicable data protection law.

10.1.5. Dissemination of Clinical Study Data

Study-related information and study results may be posted on publicly accessible clinical study databases (eg, the US website www.clinicaltrials.gov or the EU website www.clinicaltrialsregister.eu), as appropriate, and in accordance with national, regional, and local regulations.

10.1.6. Data Quality Assurance

- All participant data relating to the study will be recorded on printed CRF or eCRF unless transmitted to Alexion or designee electronically (eg, laboratory data). The Investigator is responsible for verifying that data entries are accurate and correct by physically or electronically signing the CRF.
- The Investigator must maintain accurate documentation (source data) that supports the information entered in the eCRF.
- The Investigator must permit study-related monitoring, audits, IRB/IEC review, and regulatory agency inspections and provide direct access to source data documents.
- Alexion or designee is responsible for the data management of this study including quality checking of the data.
- Study monitors will perform ongoing source data verification to confirm that data entered into the eCRF by authorized site personnel are accurate, complete, and verifiable from source documents; that the safety and rights of participants are being protected; and that the study is being conducted in accordance with the currently approved protocol and any other study agreements, ICH GCP, and all applicable regulatory requirements.
 - Remote source data verification may be employed where permitted by local regulations.
 - The scope of the source data verification will be described in detail in the Clinical Monitoring Plan.

Page 64 of 97
Alexion Confidential

• Records and documents, including signed ICFs, pertaining to the conduct of this study must be retained by the Investigator after study completion per local regulations or institutional policies. No records may be destroyed without the written approval of Alexion. No records may be transferred to another location or party without written notification to Alexion.

10.1.7. Source Documents

Source documents provide evidence for the existence of the participant and substantiate the integrity of the data collected. The Investigator or designee will prepare and maintain adequate and accurate source documents (eg, medical records, ECGs, AE and concomitant medication reporting, raw data collection forms) designed to record all observations and other pertinent data for each participant.

Data reported on the eCRF that are transcribed from source documents must be consistent with the source documents or the discrepancies must be explained. Electronic case report forms must be completed by the Investigator or designee as indicated in the site delegation log. The Investigator may need to request previous medical records or transfer records, depending on the study. Also, current medical records must be available to Alexion, Alexion delegates, and health authorities, as requested. Source documents are filed at the investigational site.

Per ICH E6 (R2) guidelines and good documentation practice requirements, source documents and study records in all media (eg, paper, electronic) must be Attributable, Legible, Contemporaneous, Original, Accurate, and Complete.

10.1.8. Study and Site Start and Closure

The study start date is the date on which the first participant is consented.

Alexion reserves the right to close the study site or terminate the study at any time for any reason at its sole discretion. Study sites will be closed after the study is completed or following the decision to close or terminate the study. A study site is considered closed when all participants have completed the End of Study or Early Discontinuation visit, all data have been collected and entered into the electronic data capture system, all required documents and study supplies have been collected and reconciled, and a study-site closure visit has been performed.

The Investigator may initiate study-site closure at any time, provided there is reasonable cause and sufficient notice is given in advance of the intended termination.

Reasons for the early closure of a study site by Alexion or Investigator may include but are not limited to:

- Failure of the Investigator to comply with the protocol, the requirements of the IRB/IEC or local health authorities, Alexion's procedures, or ICH GCP guidelines
- Inadequate recruitment of participants by the Investigator
- Decision on the part of Alexion to suspend or discontinue testing, evaluation, or development of the study drug
- Discovery of an unexpected, serious, or unacceptable risk to participants enrolled in the study

Page 65 of 97	
Alexion Confidential	

If the study is prematurely terminated or suspended, Alexion shall promptly inform the Investigators, the IECs/IRBs, the regulatory authorities, and any contract research organization(s) used in the study of the reason for termination or suspension, as specified by the applicable regulatory requirements. The Investigator shall promptly inform the participant and should assure appropriate participant therapy and/or follow-up.

10.1.9. Publication Policy

- Where possible, primary manuscripts reporting results of the primary efficacy endpoint or the final results will be submitted for publication within 12 to 18 months of the primary evaluation date or end of study, whichever is earlier.
- Investigators who participate as authors in manuscripts derived from Alexion-sponsored studies will agree to the prerequisites as outlined in the Alexion author engagement agreement prior to engaging in manuscript development.
- The Investigator agrees to submit proposals for new manuscripts (whether or not the proposed analyses are derived from protocol-specified endpoints) to Alexion for review and consideration. All manuscripts or abstracts emanating from approved proposals are to be submitted to Alexion for review before submission to the journal/society. This allows Alexion to protect proprietary information and provide comments.
 - The proprietary nature of some development work may preclude publication. In some cases, it may be necessary to delay a publication to allow Alexion to ensure protection of intellectual property.
- Primary publications, including congress and journal publications, containing the protocol-specified results of a study should occur prior to the publication of individual study site results or case reports. Alexion's policy prohibits duplicate publication, whereby the same results must not be published in multiple peer-reviewed journal manuscripts.
 - Encore congress publications may be appropriate to allow communication of research findings to relevant audience and geographical regions.
- Alexion will comply with the requirements for publication of study results as defined by the Pharmaceutical Research and Manufacturers of America and the International Committee of Medical Journal Editors and per the Alexion Publication Policy. In accordance with standard editorial and ethical practice, Alexion will generally support publication of multicenter studies only in their entirety and not as individual site data. In this case, a Coordinating Investigator will be designated by mutual agreement.
- Authorship will be determined by mutual agreement and in line with International Committee of Medical Journal Editors authorship requirements and per the Alexion Publication Policy.
- Alexion will Publish Patient Lay Summaries and include participants and/or caregivers as reviewers for readability and understanding of lay person language.

Page 66 of 97	
Alexion Confidential	

10.1.10. Good Clinical Practice Compliance

Alexion and any third party to whom aspects of the study management or monitoring have been delegated will undertake their assigned roles for this study in compliance with all applicable industry regulations, ICH GCP Guideline E6 R2, EU Directive 2001/20/EC, as well as all applicable national and local laws and regulations.

Visits to sites are conducted by representatives of Alexion and/or the company organizing/managing the research on behalf of Alexion to inspect study data, participants' medical records, and eCRFs in accordance with current GCP and respective local and (inter)national government regulations and guidelines. Records and data may additionally be reviewed by auditors or by regulatory authorities.

Alexion ensures that local regulatory authority requirements are met before the start of the study. Alexion (or designee) is responsible for the preparation, submission, and confirmation of receipt of any regulatory authority approvals required prior to release of ALXN1850 for shipment to the site.

Page 67 o	of 97
Alexion Cont	

10.2. Clinical Laboratory Tests

- The clinical safety tests detailed in Table 7 will be performed by a local laboratory or by Alexion, as indicated.
- Protocol-specific requirements for inclusion or exclusion of participants are detailed in Section 5.
- Additional tests may be performed at any time during the study as determined necessary by the Investigator or required by local regulations.
- The results of each test must be entered in the eCRF.
- Pregnancy testing: Women of childbearing potential should only be enrolled after a negative serum pregnancy test result at Screening. Urine pregnancy testing will be performed for women of childbearing potential at all subsequent timepoints specified in the SoA (Section 1.3). Additional pregnancy tests may also be performed at any time at the Investigator's discretion.

Laboratory Assessments	Parameters			
Hematology	Red blood cell count Hematocrit	Red blood cell indices Mean corpuscular vol Mean corpuscular hen %Reticulocytes Glycated hemoglobin	ume noglobin	White blood cell count with differential: Neutrophils Lymphocytes Monocytes Eosinophils Basophils Platelet count
Clinical chemistry ^b	Blood urea nitrogen Potassium Creatinine Sodium Chloride Glucose Total carbon dioxide	Aspartate aminotransf /serum glutamic-oxale transaminase Gamma glutamyltrans Alanine aminotransfer glutamic-pyruvic tran Alkaline phosphatase	oacetic sferase rase /serum saminase	Total and direct bilirubin Indirect bilirubin Total protein Albumin Calcium ^c Phosphate Magnesium
Coagulation	Prothrombin time	Partial thromboplastin	n time	International normalized ratio
Other safety laboratory tests	Parathyroid hormone, int 25-OH Vitamin D Antidrug antibodies (Ale Neutralizing antibodies (ca xion) re Alexion) Tr C: Ig He	ise of an acut action: ryptase (Alex 5b-9 (Alexion) E (Alexion)	
Other urine tests	Routine urinalysis: Speci urobilinogen, nitrite, eryt Microscopic examination menstruating] are abnorn	hrocytes, leukocyte este n (if any leukocytes, trac	erase (by dips	stick)

 Table 7:
 Protocol-Required Safety Laboratory Assessments

Laboratory Assessments	Parameters
	Further urinalysis for calcium, phosphorus, creatinine and calcium/creatinine Urine pregnancy tests (after Screening, for women of childbearing potential)
Other screening tests	Alcohol test
	Urine drug screen (to include amphetamines; barbiturates; benzodiazepines; cocaine; opiates; phencyclidine; methamphetamine; 3,4 methylenedioxy-methamphetamine; and methadone)
	FSH test (confirmation of post-menopausal state)
	HIV-1 and HIV-2 antibodies, hepatitis B surface antigen (HbsAg), anti-HBC IgG + IgM (if IgG positive) and hepatitis C virus antibodies (anti-HCV)
⁸ Only collected at Scre	Serum human chorionic gonadotropin pregnancy test (for women of childbearing potential)

 Table 7:
 Protocol-Required Safety Laboratory Assessments

^a Only collected at Screening.

^b Clinical chemistry must be fasting only at Screening.

^c Includes ionized calcium.

Abbreviations: 25-OH = 25-hydroxy; C5b-9 = terminal complement complex C5b-9; eCRF = electronic case report form; FSH = follicle-stimulating hormone; HBC = hepatitis B core antigen; HIV = human immunodeficiency virus IgG = immunoglobulin G; IgM = immunoglobulin M; PLP = pyridoxal 5'-phosphate

Investigators must document their review of each laboratory safety report.

Page 69 of 97	
Alexion Confidential	
Alexion Confidential	

10.3. Adverse Events: Definitions and Procedures for Recording, Evaluating, Follow-up, and Reporting

10.3.1. Definition of AE

AE Definition

- An AE is any untoward medical occurrence in a participant or clinical investigation participant administered a pharmaceutical product and which does not necessarily have to have a causal relationship with this treatment (ICH E2A).
- Note: An AE can therefore be any unfavorable and unintended sign (including an abnormal laboratory finding), symptom, or disease [new or exacerbated] temporally associated with the use of the study intervention, whether or not considered related to the study intervention.

Events Meeting the AE Definition

- Any abnormal laboratory test results (hematology, clinical chemistry, or urinalysis) or other safety assessments (eg, ECG, radiological scans, vital signs measurements), including those that worsen from baseline, considered clinically significant in the medical and scientific judgment of the Investigator.
- Exacerbation of a chronic or intermittent pre-existing condition including either an increase in frequency and/or intensity of the condition.
- New conditions detected or diagnosed after study intervention administration even though it may have been present before the start of the study.
- Signs, symptoms, or the clinical sequelae of a suspected drug-drug interaction.
- Signs, symptoms, or the clinical sequelae of a suspected overdose of either study intervention or a concomitant medication. Overdose per se will not be reported as an AE/SAE unless it is an intentional overdose taken with possible suicidal/self-harming intent. Such overdoses should be reported regardless of sequelae.

Events **Not** Meeting the AE Definition

- Medical or surgical procedure (eg, endoscopy, appendectomy): The condition that leads to the procedure is the AE. Situations in which an untoward medical occurrence did not occur (eg, hospitalization for elective surgery if planned before the signing the ICF, admissions for social reasons or for convenience).
- Anticipated day-to-day fluctuations of pre-existing disease(s) or condition(s) present or detected at the start of the study that do not worsen.
- A medication error (including intentional misuse, abuse, and overdose of the product) or use other than what is defined in the protocol is not considered an AE unless there is an untoward medical occurrence as a result of a medication error.
- Cases of pregnancy that occur during maternal or paternal exposure to study intervention are to be reported within 24 hours of Investigator/site awareness. Data on fetal outcome and breastfeeding will be collected for regulatory reporting and safety evaluation.
- Any clinically significant abnormal laboratory findings or other abnormal safety assessments which are associated with the underlying disease, unless judged by the Investigator to be more severe than expected for the participant's condition.
- The disease/disorder being studied or expected progression, signs, or symptoms of the disease/disorder being studied, unless more severe than expected for the participant's condition.
- Situations in which an untoward medical occurrence did not occur (social and/or convenience admission to a hospital).

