8.3. Adverse Events and Serious Adverse Events

The definitions of AEs and SAEs can be found in Section 10.3. All AEs will be reported to the Investigator or qualified designee by the participant.

The Investigator and any qualified designees are responsible for detecting, documenting, and recording events that meet the definition of an AE or SAE and remain responsible for following up AEs that are serious, considered related to the study intervention or study procedures, or that caused the participant to discontinue the study drug (see Section 7).

Procedures for recording, evaluating, follow-up, and reporting AEs and SAEs are outlined in Section 10.3.

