8.3.5. Disease-Related Events and/or Disease-Related Outcomes Not Qualifying as AEs or SAEs

Any increase on frequency and/or intensity in the signs/symptoms of the disease under study will be reported as AEs.

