9.4.2. Safety Analyses

The primary objective of the study is to assess the safety and tolerability of ALXN1850. The endpoints to support the primary objective include incidence of TEAEs and treatment-emergent serious adverse events (TESAEs). The incidence of TEAEs and TESAEs will be summarized by System Organ Class (SOC) and Preferred Term by administration and cohort overall, by severity, and by relationship to study intervention. Adverse events will be categorized by the type of administration being received at the date of onset (ie, IV or SC). Treatment-emergent AEs and TESAEs resulting in withdrawal from the study will be listed. Participants having multiple AEs within a category (eg, overall, SOC, Preferred Term) will be counted once in that category. For severity tables, a participant's most severe event within a category will be counted. Adverse events of special interest will be analyzed similarly.

Changes from baseline in vital signs and laboratory assessments (as displayed in Table 7) will be summarized by visit for each cohort. Laboratory parameter values will be graded based on the National Cancer Institute CTCAE grading for severity (v5.0, published 27 Nov 2017). Shift tables by treatment group will be produced for these laboratory parameters. These tables will summarize the number of participants with each baseline grade relative to the normal ranges and changes to the worst highest grade assessed postdose during the study.

Electrocardiogram parameters will be measured at the specified time points, including heart rate, PR, RR, QRS, QT, and QTcF intervals. The average of the triplicate ECG readings at the time points collected will be calculated, and changes from pretreatment baseline values will be assessed.

An outlier analysis will be performed that will summarize the frequency and percentage of participants who meet any of the following outlier criteria at each visit.

- QT, QTcF interval > 450 msec
- QT, QTcF interval > 480 msec
- QT, QTcF interval > 500 msec
- QT, QTcF interval increases from baseline > 30 msec
- QT, QTcF interval increases from baseline > 60 msec

Physical examination results will be classified as Normal, Abnormal Not Clinically Significant (NCS), Abnormal Clinically Significant (CS), and Not Examined. The results will be summarized by visit for each administration.

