10.3.2. Definition of SAE

If an event is not an AE per definition above, then it cannot be an SAE even if serious conditions are met (eg, hospitalization for signs/symptoms of the disease under study, death due to progression of disease).

An SAE is defined as any untoward medical occurrence that, at any dose:
1. Results in death
2. Is life-threatening
The term "life-threatening" in the definition of "serious" refers to an event in which the participant was at risk of
death at the time of the event. It does not refer to an event, which hypothetically might have caused death, if it
was more severe.
3. Requires inpatient hospitalization or prolongation of existing hospitalization
In general, hospitalization signifies that the participant has been detained (usually involving at least an overnight
stay) at the hospital or emergency ward for observation and/or treatment that would not have been appropriate in
the physician's office or outpatient setting. Complications that occur during hospitalization are AEs. If a
complication prolongs hospitalization or fulfills any other serious criteria, the event is serious. When in doubt as
to whether "hospitalization" occurred or was necessary, the AE should be considered serious.
Hospitalization for elective treatment of a pre-existing condition that did not worsen from baseline is not
considered an AE.
4. Results in persistent disability/incapacity
• The term disability means a substantial disruption of a person's ability to conduct normal life functions.
This definition is not intended to include experiences of relatively minor medical significance such as
uncomplicated headache, nausea, vomiting, diarrhea, influenza, and accidental trauma (eg, sprained ankle)
which may interfere with or prevent everyday life functions but do not constitute a substantial disruption.
5. Is a congenital anomaly/birth defect
6. Other situations:
• Medical or scientific judgment should be exercised in deciding whether SAE reporting is appropriate in
other situations such as important medical events that may not be immediately life-threatening or result in
death or hospitalization but may jeopardize the participant or may require medical or surgical intervention to
prevent one of the other outcomes listed in the above definition. These events should usually be considered
serious.
• Examples of such events include invasive or malignant cancers, intensive treatment in an emergency room

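### The protocol gives two rules for recording worsening of hypophosphatasia that the investigator judges expected, so the primary TEAE/TESAE count can depend on which section a site follows

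*Protocol*

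**What the plan says.** Protocol 8.3.5 states: "Any increase on frequency and/or intensity in the signs/symptoms of the disease under study will be reported as AEs". It makes no exception for worsening that was expected. The heading above that sentence points the other way: "Disease-Related Events and/or Disease-Related Outcomes Not Qualifying as AEs or SAEs".

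Protocol 10.3.1 has two lists. The list of events that meet the AE definition agrees with the 8.3.5 sentence: "Exacerbation of a chronic or intermittent pre-existing condition including either an increase in frequency and/or intensity of the condition". The list of events that do not meet it contains "The disease/disorder being studied or expected progression, signs, or symptoms of the disease/disorder being studied, unless more severe than expected for the participant's condition". A separate bullet in that second list covers abnormal laboratory and other safety findings "which are associated with the underlying disease, unless judged by the Investigator to be more severe than expected for the participant's condition".

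Protocol 10.3.2 opens: "If an event is not an AE per definition above, then it cannot be an SAE even if serious conditions are met". Its examples are hospitalization for signs or symptoms of the disease and death from its progression.

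Protocol 8.3 says only that "The definitions of AEs and SAEs can be found in Section 10.3". SAP 9.1 repeats the general AE definition, which covers disease that is new or exacerbated, and defines TEAEs as AEs that start or worsen from the first dose to the final follow-up visit. It has no rule for worsening of HPP itself. The single primary endpoint in both documents is the incidence of TEAEs and TESAEs.

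**The concern.** Suppose a participant's bone pain increases after a dose, and the investigator regards the increase as within the expected course of HPP. A site working from 8.3.5 records an AE. A site working from the not-meeting list in 10.3.1 records nothing, and under 10.3.2 a resulting hospital stay would not be an SAE.

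This is a first-in-human, open-label study without a control arm. Protocol 2.2.1 attributes pain, fractures, muscle weakness and impaired renal function to HPP, so a drug effect on symptoms could resemble the disease. Causality is assessed for each recorded AE (10.3.4). Under the exclusion, the investigator decides whether an event was expected before any related/not related judgement is made, and an excluded event never receives one. The SAP cannot recover an event that was not entered.

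Two oversight provisions also rest on the TESAE label: suspension of the study for severe or life-threatening TESAEs (opening text of Section 7) and the ad hoc SRC meeting required within 48 hours of a treatment-emergent SAE (9.6).

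**Working it through.** The plan has no figure to reproduce: the sample size is empiric and no hypotheses are planned (Protocol 9.1 and 9.2). The check is a comparison of texts, followed by arithmetic for scale.

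**Step 1. Apply each rule to each class of event.**

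| HPP sign or symptom after the first dose | 8.3.5 sentence | 10.3.1 not-meeting list | Conflict |
|---|---|---|---|
| Stable, or fluctuating without worsening | Not covered | Not an AE | No |
| Increases, and is worse than expected for this participant | AE | AE | No |
| Increases, and is judged expected for this participant | AE | Not an AE | Yes |

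Only the third row is disputed.

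**Step 2. Can the texts be harmonised?** If every increase counted as more severe than expected, the conflict would vanish, but the words on expected progression would then have no content. Nor can the bullet be read as covering only stable disease, because another bullet in the same list already removes day-to-day fluctuations that do not worsen. The disease bullet adds something only if it removes some worsening, which is what 8.3.5 includes.

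**Step 3. Is there a tie-breaker?** The pointer in 8.3 sends the reader to 10.3 for definitions but gives it no precedence over 8.3.5. Administrative Change Letter #6 deals with postdose timepoints, site evaluations and hypersensitivity laboratory tests. SAP 9.1 does not address the question.

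**Step 4. Carry-over to SAEs.** By 10.3.2, a third-row event under the 10.3.1 reading cannot be an SAE even if it leads to hospitalization. The instruction there to treat doubtful hospitalizations as serious speaks of an AE, so it does not clearly reach an excluded event.

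**Step 5. Scale.** Inputs: about 5 participants per cohort and about 15 in total (Protocol 1.1), with percentages taken over the Safety Set (SAP 9.1). One participant whose only TEAE is a third-row event shifts participant-level incidence by 1/n:

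- cohort of 5: 1/5 = 20.0 points
- cohort with only 3 treated: 1/3 = 33.3 points
- all 15: 1/15 = 6.7 points

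The documents give no probability p that a participant is of this kind. Under assumed values, the chance of at least one is 1 − (1 − p)^n:

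| Assumed p | n = 5 | n = 15 |
|---|---|---|
| 0.05 | 0.23 | 0.54 |
| 0.10 | 0.41 | 0.79 |
| 0.20 | 0.67 | 0.97 |
| 0.30 | 0.83 | 0.995 |

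These are assumptions, not estimates. A p near zero, and so no shift, is also compatible with the documents.

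**The case against.** The other side has a good deal on scope and consequence.

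- *Most of the text points one way.* The 8.3.5 sentence, the meeting list in 10.3.1 and the reference to exacerbated disease in the general definition all favour recording. This helps in choosing a repair, but it does not cancel an explicit exclusion in the definitions section.
- *Stopping rules.* A reader might infer that the stopping rules as a whole are undermined. The documents do not support that. The AE-based rules in 7.1.1 and 7.1.2 require an event related to study drug, and an event regarded as expected HPP would probably be called not related under 10.3.4. The exposed provisions are the TESAE suspension and the 48-hour SRC trigger, and both need a serious event. The suspension sentence states no relatedness condition of its own, but it follows a general sentence limiting the rule sets to related events. If that limit applies to it, only the SRC trigger is clearly exposed.
- *SRC visibility.* A reader might infer that the committee would be blind to these participants. It also reviews laboratory, ECG and vital-sign data (6.6.1), so the gap is mainly in symptoms.
- *Ectopic calcification.* A reader might fear that this listed risk could be absorbed as disease. It is not among the HPP manifestations in 2.2.1. It is sought by scheduled eye examination and renal ultrasound (8.2.8, 8.2.9), and SAP 9.6 and 9.7 list those results whatever the AE coding.
- *Laboratory findings.* A reader might extend the conflict to the laboratory bullet in 10.3.1 and to 8.2.4. Those two agree with each other, and 8.3.5 covers signs and symptoms only.
- *Size.* A participant with any other TEAE already counts, so overall incidence does not move. Participants are not anticipated to need enzyme replacement after the study (5.1), and recent fracture and unstable illness are excluded (5.2). The last visit is Day 78 or Day 85. Such events may be few or absent.

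All of these limits stand. The contradiction for expected worsening remains.

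**Conclusion.** The protocol contradicts itself on whether an increase in HPP signs or symptoms that the investigator judges expected is an AE, and nothing in the protocol or SAP settles it. Confidence in the textual conflict is high. The recorded primary endpoint, and the TESAE-based triggers to the extent described above, can therefore depend on the section a site follows.

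The effect on the endpoint is unknown. The 20-point and 6.7-point figures assume cohorts of 5, 15 treated in total, and a participant with no other TEAE. A reader might multiply them by a guessed number of affected participants and quote a range of bias. The documents give no rate to support that, and zero is possible. With groups this small, however, one classification decision is visible in the table, and the correction is cheap. It should be made.

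**What to change.** Reconcile three places into one recording rule: 8.3.5 including its heading, the disease signs-and-symptoms bullet in the not-meeting list of 10.3.1, and the examples at the start of 10.3.2. One way is to limit the 10.3.1 bullet to disease signs and symptoms that do not increase in frequency or intensity. Every increase is then recorded as an AE, as 8.3.5 and the meeting list already state, and the related/not related field carries attribution. If the sponsor prefers the 10.3.1 exclusion, the 8.3.5 sentence and the meeting list must change instead; the two rules should not both remain.

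Align SAP 9.1 with a sentence stating how worsening of HPP is counted. The laboratory bullet in 10.3.1 and the text in 8.2.4 can stay.

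The cost is wording in an amendment or administrative letter and a reminder to sites. The downside of the suggested rule is a possibly higher reported TEAE count.
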